9. SCHEDULE OF ASSESSMENTS

Overview of Visits

All participants will undergo eligibility screening, informed consent and randomization procedures.

Follow-up in randomized participants will occur at 1.5, 3, 6, and 12 months following randomization during the first year and every 6 months thereafter, with clinic visits, phone follow-up, and other testing as described below (See [Table 2](#) for complete assessment schedule). The schedule of assessments ([Table 2](#)) specifies the preferred method of contact for each visit. Six-month visits may be via telephone or email, depending on participant stability, risk factor control, and the participant's distance from the clinic ("geography") ([see Table 2](#)). In the event that a scheduled clinic visit is not possible, to ensure participant follow-up other forms of contact should be used, such as telephone, email, communication from a personal physician, other allied health professional, or family member, or review of electronic health record or public records. After the first year, participants will be followed every 6 months until the end of the trial, at which time sites will be notified to perform a closeout visit.

Dependent on additional funding, telephone or email follow-up every 6 months or ascertainment of database information on vital status may continue after all clinic visits have been completed, unless prohibited by local regulations. At these long-term follow-up contacts, information on current health and medications, and interval hospitalizations will be collected.

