Withdrawal from the Study: Complete and accurate follow-up is extremely important for the duration of the study. The participant, however, may decline to continue with their assigned management strategy at any time. This does not constitute withdrawal from the study. Participants will continue to be followed per the assessment schedule. If at any time the subject refuses to continue with study visits, every attempt will be made to continue contact by telephone, written communication, email, by proxy contact with family, friends, or allied health care providers, or record review to determine if outcome events have occurred, unless the subject specifically refuses such follow-up. National databases that record deaths will be used to ascertain vital status, unless prohibited by local regulations. The reason for (and the level of) withdrawal will be documented for all subjects withdrawn from the study or for those having limited follow-up. The subject must specify in writing what follow-up (s)he will allow, if any, at the time of withdrawal discussion.

Quality of Life (QOL) and Economics Overview

A brief set of items capturing selected interval angina and dyspnea symptoms QOL (Brief/Symptom/QOL) will be collected by the site coordinator and entered into the EDC study database at every study visit through 36 months and then each 6 months until the final closeout ISCHEMIA-CKD visit. A Hospitalization assessment as part of the main study EDC database will be collected on all randomized ISCHEMIA-CKD participants at each follow-up study interval throughout the trial to provide a measure of resource utilization.

Table 2 Schedule of Study Assessments and Procedures (see Manual of Operations for visit windows)

	Screening visit	CCTA visit	Randomization visit (Baseline Visit)	Catheterization & PCI or CABG	Follow up									
					1.5m ^A Visit 1	3m ^A Visit 2	6m ^B Visit 3	12m ^A Visit 4	18m ^B Visit 5	24m Visit 6	30m ^B Visit 7	36m ^C Visit 8	Frequency beyond 36 months	
Eligibility screen	X													
Informed consent (including biorepository consent if applicable)	X													
Creatinine and pregnancy test ^D	X													
Medical History/Medical Status	X		X		X	X	X	X	X	X	X	X	X	Q6m
Cardiovascular medications	X		X		X	X	X	X	X	X	X	X	X	Q6m
Transmit Stress Test to Core Lab ^E	X													
NYHA* and CCS class**	X		X		X	X	X	X	X	X	X	X	X	Q6m
Release for medical records signed			X				X			X		X		Q12m
Safety assessment ^F		X		X										

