- For enrolled participants ischemia tests will be transferred electronically to the appropriate core laboratory. (see [section 5.4](#))

Randomization visit (Baseline Visit) (targeted within 15 days of participant’s consent)

- Medical history including CV medications will be documented
- NYHA and CCS class (see MOO)
- Brief symptoms/QOL assessment will be collected (prior to actual randomization)
- Modified Morisky medication adherence survey (see MOO)
- Vital signs, height and weight will be measured
- 12 lead ECG will be performed and sent to ECG core lab; stress ECG, and symptom, and hemodynamic results will be sent to ECG core lab
- Results of routine laboratory tests performed within 6 months of visit will be recorded, including HbA1c for diabetic participants. If these test results are not available a blood draw for routine laboratory tests will be done at this visit (see MOO)
- Baseline blood draw for biomarker/genetics biorepositories

- Eligible participants will be randomized to INV or CON strategies via the IVRS/IXRS system. (These participants are considered randomized)
- Participants randomized to INV strategy should target to undergo catheterization, with optimal revascularization to be completed within a target of 30 days from randomization
- PACE will be implemented for all participants
- Initiate OMT in all randomized participants according to guideline recommendations and study algorithms

Cath and Revascularization for participants randomized to INV strategy (protocol assigned); also applies to all revascularization procedures for participants in both management strategies

- For protocol assigned cardiac cath and revascularization (INV strategy participants), target completion within 30 days of randomization
- Revascularization to be performed as per Optimal Revascularization Therapy (ORT) (refer to MOO)
- For participants undergoing PCI
 - 12 lead ECG to be performed post-PCI at 60 ± 30 minutes, and as needed for chest pain
 - Blood draw for both CK-MB and troponin before PCI, and at 8-16 ± 2 hours post-PCI or at hospital discharge, whichever comes earlier, whenever possible
 - All pre- and post-procedure biomarker measurements that are obtained should be recorded on eCRF
- For participants undergoing CABG
 - 12 lead ECG to be performed on day 3 post-CABG or at hospital discharge whichever comes earlier, and as needed for chest pain

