11. STATISTICAL CONSIDERATIONS AND ANALYSIS PLAN

11.1 Sample Size Determination and Statistical Power

11.1.1 Summary of Power and Precision

As shown in Tables 3 and 4 below, the planned sample size of approximately 1,000 randomized participants will result in an estimate of the hazard ratio that differs from the true hazard ratio by no more than a factor of 1.19 with 95% probability and will yield power $\geq 80-95\%$ for comparing the primary composite endpoint across the two randomized groups assuming the 4-year cumulative rate of the primary composite endpoint is 60% in participants randomized to CON strategy and is less by a factor of 15% to 19% (relative reduction) in participants randomized to INV strategy. Power and precision under other assumptions are summarized in [Table 5](#) and [Table 6](#) below.

CON anticipated 4-year event rate	Power		
	$\Delta = 0.15$	$\Delta = 0.17$	$\Delta = 0.19$
Event %			
45%	56	67	76
50%	64	75	84
55%	73	83	90
60%	81	90	95
65%	88	95	98
70%	94	98	99

NOTE: Δ denotes relative reduction in 4-year event rate in INV vs. CON groups. **Assumptions:** Two-sided log-rank test with $\alpha = 0.05$; 500 participants per group; average follow-up 3.7 years; loss-to-follow-up 1% per year; survival times follow exponential distribution.

CON anticipated 4-year event rate	Margin of Error (MOE)		
	$\Delta = 0.15$	$\Delta = 0.17$	$\Delta = 0.19$
Event %			
45%	1.22	1.22	1.23
50%	1.21	1.21	1.21
55%	1.20	1.20	1.20
60%	1.19	1.19	1.19
65%	1.18	1.18	1.18
70%	1.17	1.18	1.18

NOTE: Margin of Error is the anti-log of the expected half-width of the 95% confidence interval for the log-hazard ratio. Assumptions: Based on a univariable Cox model with a binary treatment indicator and Wald-type 95% confidence intervals.

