11.2 Statistical Analysis Plan

All major treatment comparisons between the randomized groups will be performed according to the principle of "intent-to-treat;" that is, participants will be analyzed (and endpoints attributed) according to the randomized strategy, regardless of subsequent invasive testing or treatment. Statistical comparisons will be performed using two-sided significance tests. A statistical analysis plan will be finalized before trial completion and data analysis.

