11.2.4 Quality of Life (QOL) Analysis

All QOL comparisons will adhere to the intention-to-treat principle. For each QOL measure examined in this study, data analysis will proceed in several stages. First, we will provide simple descriptive and comparative analyses by intention-to-treat. Statistical power estimates for this part of our analysis, based on data collected in the COURAGE trial, show that we should have in excess of 99% power to detect $\frac{1}{4}$ SD differences in our 3 principal QOL measures. Second, we will examine changes over time from baseline and identify the major determinants of those changes using regression analysis. Since there is currently no consensus in the statistical literature about the best way to deal with the multiple comparisons problem arising from testing each individual scale separately, we propose two complementary approaches. First, we will pre-specify the angina frequency and QOL scales from the SAQ as the CAD-specific measures of primary interest and assign all other comparisons to a secondary (descriptive) status. Second, we will employ a mixed model methodology that makes use of all available QOL data at each study assessment point to model the time profile (fixed effect). Using the fitted model, we can

estimate the overall difference in the QOL measures as well as test the global hypothesis of no difference over time. We can also estimate the difference in the areas under the two QOL treatment curves (and test the hypothesis of no difference, on average). In addition, we can estimate differences in QOL at the end of the study or at intermediate points. Lastly, to address the possibility that international differences in QOL exist despite our use of extensively culturally validated instruments, we will examine interactions between key QOL outcomes, treatment, and geographic region.

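### The 99% power stated for quarter-SD quality-of-life differences lacks a stated basis; the simple comparison it is attached to gives 97.7% at best with 500 per group

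*Combined protocol and SAP*

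**What the plan says.** Section 11.2.4 sets out the quality-of-life analysis in stages. The first is described this way: "First, we will provide simple descriptive and comparative analyses by intention-to-treat". The next sentence ties a power statement to that part of the analysis. It says that estimates drawn from the COURAGE data "show that we should have in excess of 99% power to detect" differences of a quarter of a standard deviation in three principal measures. Change from baseline with regression comes second. The mixed model that uses all visits is described later and is not linked to the power figure.

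The sentence states no sample size, alpha, visit, test, covariates, correlation or allowance for deaths. The nearest inputs are elsewhere. The primary-endpoint power table in Section 11.1.1 assumes "500 participants per group". Section 11.2 says: "Statistical comparisons will be performed using two-sided significance tests". An alpha of 0.05 is given in Section 11.2.1, for the primary endpoint only.

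**The concern.** The two SAQ scales carry the first-named secondary objective, so readers will use this sentence to judge how much weight a null quality-of-life result can bear. For a quarter-SD effect and a simple two-group comparison, power depends only on the number assessed, alpha and any variance reduction from a covariate or from averaging visits. Putting the plan's own group size into the plain comparison does not give 99%.

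The population also has high expected mortality, and participants who die contribute no later SAQ score. The number assessed therefore falls with each visit. Without a named visit and model, a reader cannot tell for which comparison the stated power holds.

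**Working it through.** **Inputs.** Effect 0.25 SD (Section 11.2.4); 500 per group (Section 11.1.1); two-sided testing (Section 11.2); alpha 0.05, assumed to carry over from the primary endpoint; 4-year mortality above 50% (Section 2, a background figure for advanced CKD); exponential survival (assumed in Section 11.1.1 for the primary endpoint, used here for deaths). Correlations are assumptions, because the documents give none.

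**Formula.** With n assessed per group and baseline correlation r (r = 0 if unadjusted):

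Power = Φ(0.25·√(n/2)/√(1 − r²) − 1.960)

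**The plan's figure on its plain reading.** n = 500, r = 0: 0.25·√250 = 3.953; 3.953 − 1.960 = 1.993; Φ(1.993) = 97.7%. The noncentral t gives the same to one decimal. A two-sided alpha of 0.10 (critical value 1.645) gives 98.95%, still under 99%.

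**What would give 99%.**
- Group size, unadjusted: 2·((1.960 + 2.326)/0.25)² = 588 per group.
- Effect size at 500 per group: 4.286/√250 = 0.271 SD.
- Baseline adjustment with complete data: r = √(1 − 500/588) = 0.39. At r = 0.4 power is 99.1%; at r = 0.5 it is 99.5%.
- Mean of the four first-year visits, with within-person correlation c: the variance factor (1 + 3c)/4 must be at most 500/588 = 0.850, so c is at most 0.80. At c = 0.6 power is 99.7% with 500 per group.

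**Effect of deaths.** Alive per group at a given month = 500·(1 − m)^(months/48), where m is 4-year mortality. No other missing forms are assumed. At 12 months:

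| 4-year mortality m | Alive per group | Unadjusted power | Power at r = 0.5 | r needed for 99% |
|---|---|---|---|---|
| 30% (assumed) | 457 | 96.6% | 99.2% | 0.47 |
| 40% (assumed) | 440 | 96.0% | 99.0% | 0.50 |
| 50% (lower bound in Section 2) | 420 | 95.2% | 98.7% | 0.53 |
| 55% | 410 | 94.7% | 98.5% | 0.55 |

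Adding the 1% per year loss from Section 11.1.1 to the 50% row leaves 416 per group and 95.0% unadjusted.

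The table stops at 55% because of the primary-endpoint base case, "assuming the 4-year cumulative rate of the primary composite endpoint is 60% in participants randomized to CON strategy", reduced by 15% to 19% in the invasive group. That puts death or MI at 60%·0.81 = 48.6% to 60%·0.85 = 51% in that group, and at (60 + 48.6)/2 = 54.3% to (60 + 51)/2 = 55.5% overall. Deaths alone cannot exceed this.

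**Choice of visit.** An earlier visit does not close the gap. At 1.5 months, the first follow-up visit, 494 to 489 per group are alive under 30% to 50% mortality, and unadjusted power is 97.6% to 97.4%.

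**The case against.** The strongest reply is that the figure is under-documented, not wrong. The wording of the first stage names no test and does not rule out a baseline covariate or several visits. Plain two-sample power for a standardized effect needs no outside data, so the reference to COURAGE is compatible with a correlation or completeness estimate having been used, although those data may only have supplied standard deviations. Ordinary assumptions do pass 99%, as shown above; the mean of four visits at a within-person correlation of 0.6 still gives 99.1% with 420 per group. The data for either approach are planned: at baseline, "Brief symptoms/QOL assessment will be collected (prior to actual randomization"), and afterwards the brief assessment "will be collected by the site coordinator and entered into the EDC study database at every study visit through 36 months". Section 11.2.4 itself goes on to regression on change and a mixed model.

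Much of this stands. A reader might infer that the sponsor miscalculated. The documents do not support that, because the underlying calculation is not shown. What remains is that the sentence attaches its figure to the simple comparison, and on the plain reading of that comparison the figure is not delivered.

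A reader might also take 95% to 97% as the plan's own 12-month power. It is not. The mortality stated in Section 2 gives at most 95.2%, and the values of 96.0% and 96.6% require assumed 4-year mortality of 40% and 30%, which appear nowhere in the documents. Trial exclusions could make such values plausible, but they would have to be stated as assumptions.

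**Conclusion.** The point holds as a minor one. The stated power is unsupported for the analysis it is attached to. An unadjusted single-visit comparison has 97.7% power at best, and at 12 months about 95% or slightly less under the plan's own mortality figure. These results rest on 500 per group, an assumed two-sided 0.05 for quality of life, exponential mortality and no missing forms beyond deaths, except where the 1% loss is added.

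It would be wrong to conclude that the SAQ comparisons are underpowered. Power near 95% for a quarter-SD effect is high, the sample size rests on the primary endpoint, and no trial conclusion turns on the gap between 95% and 99%. What the reader lacks is the visit, number assessed, model and correlation for which the stated figure is true.

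**What to change.** In Section 11.2.4, specify that the first-stage treatment comparison of the SAQ scales is adjusted for the baseline SAQ score, and restate the power for one named visit and model with the number assessed, alpha and assumed correlation. For example: 500 per group, two-sided 0.05, quarter-SD difference; complete data, 97.7% unadjusted and 99.1% with baseline correlation 0.4; at 12 months with 50% 4-year mortality (about 420 per group alive), about 95% unadjusted and 98.7% with baseline correlation 0.5. If the 99% figure came from adjustment or repeated visits, say so and give the correlation used.

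The cost is one paragraph and no new data collection, since the baseline score is already obtained before randomization. The stated figure may become slightly less favourable, a mortality and a correlation assumption must be written down, and a rule for missing baseline scores is needed.

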11.2.5 Health Economics Analysis

The health economic analyses for ISCHEMIA-CKD will consist of a cost-effectiveness analysis.

The cost-effectiveness analyses will estimate the incremental cost required to add an extra life year with the INV strategy group relative to CON strategy group. In secondary analyses, we will incorporate utility weights to estimate the incremental cost per quality adjusted life year gained with the INV strategy relative to CON strategy. These analyses will be conducted from a societal perspective and will use a lifetime horizon so that the estimated incremental cost-effectiveness and cost-utility ratios can be compared with societal benchmarks. We will also calculate within-trial cost-effectiveness/cost-utility ratios, although these ratios are limited in their value due to their failure to account for long-term benefits and costs and the absence of comparative benchmarks. Cost will be adjusted for inflation, and both costs and life expectancy will be discounted to present value at a 3% annual discount rate. Plots of cost-effectiveness acceptability curves indicating the probability that the intervention is cost-effective for a range of willingness-to-pay thresholds will be done. Extensive sensitivity analyses will be performed.

11.2.6 Interim Analysis

For ethical reasons, interim examination of clinical endpoints and key safety events will be performed at regular intervals during the course of the trial. An independent Data and Safety Monitoring Board (DSMB) appointed by the NHLBI will monitor participant safety and to review performance of the trial ([see 13.1](#)). The primary objective of these interim analyses is to ensure the safety of the participants enrolled in the trial and evaluate the accumulating endpoint data by treatment group to test for possible differences favoring either of the two randomized management strategies. In addition, interim monitoring will involve a review of participant recruitment, compliance with the study protocol, status of data collection, an assessment of whether control group event rates are consistent with the rates hypothesized in the sample size calculations, and other factors which reflect the overall progress and integrity of the study. Because interim analyses may occur when adjudication of an event is in progress, the interim analyses will be based primarily on adjudicated events and secondarily on all best available events, i.e., as adjudicated by CEC if present or as eCRF/Investigator defined if the event has not yet been adjudicated by CEC. The results of the interim analyses and status reports will be carefully and confidentially reviewed by the DSMB. Detailed plans for interim monitoring will be documented in a separate DSMB analysis plan.

Interim comparisons by management strategy will focus on all-cause mortality and the primary composite endpoint (death and MI). Cox-proportional hazard models with treatment as the

covariate will be used for the analysis. Estimates of hazard ratios and 95% confidence intervals comparing the INV and CON strategies will be reported. To account for repeated significance testing of the accumulating data, the group sequential method of Lan and DeMets³⁵ will be used as a guide for interpreting these interim analyses. Monitoring boundaries for each endpoint will be based on a two-sided symmetric O'Brien-Fleming type spending function with an overall two-sided significance level of $\alpha = 0.05$. The O'Brien-Fleming approach requires large critical values early in the study but relaxes (i.e., decreases) the critical value as the trial progresses.³⁶ These proposed monitoring boundaries are intended as a guide for interpreting the interim analyses and not as a rule for early termination.

An additional key parameter for interim monitoring will be the frequency of early catheterization among participants randomized to the CON strategy. Such catheterizations will be classified according to (1) whether the catheterization was allowed by the protocol (e.g. for documented refractory symptoms) and (2) whether the catheterization was preceded by a nonfatal primary endpoint event (i.e., MI). A pattern of frequent early catheterization in CON participants without prior endpoint events would suggest that the study may have difficulty achieving high statistical power. Moreover, if this was due to frequent protocol violations, then a finding of no treatment effect may be challenging to interpret. To address these concerns, rates of early catheterization in the CON group will be analyzed and reported, with a focus on estimating the probability that a CON participant will undergo catheterization within a specified time interval and before an endpoint event. To obtain this probability, the distribution of "time from randomization to catheterization" for CON participants will be estimated using the cumulative incidence function method for competing risks.³⁷ For this latter analysis participant follow-up will be censored at the last contact date or terminated after the participant's first primary endpoint event, whichever occurs first.

Judgment concerning the continuation of the study will involve not only the magnitude of observed differences between randomized strategies and degree of statistical significance, but also careful consideration of many other important factors including the need for precise parameter estimation, the overall progress and integrity of the trial (including the frequency of catheterization in the CON group, as discussed above), and information available from other studies at the time of DSMB deliberations. If a stopping boundary is crossed early in the trial, this result should be tempered by the knowledge that revascularization may result in early hazard, but long-term benefit. Although we hypothesize that outcomes will be improved by the INV strategy, it should be emphasized that a small treatment effect for the primary endpoint is not necessarily a negative result for the study. Indeed, evidence suggesting absence of a large benefit from the invasive strategy would be highly important to future guidelines and clinical practice. However, a large sample size is required in order to derive such evidence. If the study were to be stopped early with less than the full sample size, the lack of statistically significant difference may be accompanied by wide confidence intervals and no clear conclusion might be possible. The DSMB will incorporate this perspective along with other considerations when making recommendations about continuation.

